**IND number:**

Not applicable

**IDE:** non-significant risk (NSR) investigational device that meets the abbreviated Investigational Device Exemptions (IDE) requirements at 21 CFR 812.2(b)

## I. Objectives

- 1) To determine the effects of tDCS on subjective measures of sleepiness in night-shift workers with shift work disorder.
- 2) To determine the effects of transcranial direct current stimulation (tDCS) on vigilance in night-shift workers with shift work disorder.

The objectives of this study are to determine if active tDCS treatment will improve vigilance and subjective measures of sleepiness in patients with shift work disorder. This is a preliminary, single-arm efficacy study which will serve as the basis of a larger, confirmatory trial if the findings are positive.

The risks associated with this study are minimal compared to the potential benefits. Knowledge about the effects of tDCS on vigilance and subjective sleepiness would be an important advance in the care of patients suffering from shift work disorder.

## II. Background and Rationale

Shift Work Disorder (SWD) is a circadian rhythm sleep disorder characterized by complaints of insomnia during hours allotted for sleep or excessive daytime sleepiness that occur during work hours that are scheduled during the usual sleep period. SWD has been estimated to affect 10-23% of the approximately 22 million Americans currently estimated to be shift workers. Among night-shift workers, the prevalence of SWD is estimated to be about 14%. SWD is considered a public health risk, as the impaired functional ability due to excessive sleepiness in persons with SWD may result in impaired occupational performance. Excessive sleepiness associated with SWD has been shown to be associated with impairments in cognition and psychomotor performance, which in turn may contribute to increased accidents during work and motor vehicle crashes during the morning commute. One-third of night workers admit to regularly nodding off or falling asleep at least once a week while working and half admit to falling asleep while commuting. About one third of nurses are estimated to have SWD.

While there are two medications (modafinil and armodafinil) approved by the Food and Drug Administration (FDA) for sleepiness during the work hours for those with SWD, they are associated with adverse events. Caffeine plus naps reduces sleepiness during the night shift, but the quality of evidence is considered low. Therefore, there is a need to develop non-pharmacologic treatment strategies for sleepiness related to SWD.

Multiple recent studies have used transcranial direct current stimulation (tDCS) as a novel therapy for central nervous system disorders including depression, anxiety, Parkinson's disease, and chronic pain. tDCS is a form of noninvasive, painless, brain stimulation that uses a mild direct electrical current passed between electrodes on the scalp to modify neuronal membrane resting potential in a polarity dependent manner, elevating or lowering neuron excitability in a region. It has several advantages over other brain stimulation techniques because it is noninvasive, painless and safe. It is also easy to administer and the equipment is easily portable. The most common side effect of tDCS is a slight itching or tingling on the scalp. Importantly, no studies thus far have provided evidence that tDCS produces more than a minimal risk. **An updated review that consolidated evidence on the safety of tDCS found that to date, the use**

**of conventional tDCS protocols in human trials ( $\leq 40$  min,  $\leq 4$  milliamperes,  $\leq 7.2$  Coulombs) has not produced any reports of a Serious Adverse Effect or irreversible injury across over 33,200 sessions and 1000 subjects with repeated sessions. This review included a wide variety of subjects, including persons from potentially vulnerable populations. In addition, several studies have shown that tDCS can be used safely in the home environment.**

Thus, tDCS is a non-significant risk (NSR) investigational device that meets the abbreviated Investigational Device Exemptions (IDE) requirements at 21 CFR 812.2(b) addressing labeling, IRB approval, informed consent, monitoring, records, reports, and prohibition against promotion for an NSR device study. An expert panel has stated that in the US, IRBs overwhelmingly designate tDCS trials as non-significant risk.

Studies using tDCS have demonstrated improvements in vigilance and cognitive function under conditions of sleep deprivation and in a case of a patient with organic hypersomnia. These studies suggest potential benefit in those with sleepiness related to SWD. Our hypothesis is that patients with sleepiness related to SWD will demonstrate improvements in vigilance and self-reported sleepiness as co-primary outcomes after receiving active stimulation.

### **III. Procedures**

#### **A. Research Design**

This is a single-arm preliminary study involving those with SWD.

Informed consent will be obtained from all participants. If the subject is agreeable, the consent form will be sent to them via mail or electronically so that they will have the opportunity to read the document ahead of time.

A separate informed consent for the purpose of screening potential candidates will be obtained.

#### **B. Subject Selection:**

##### 1. Inclusion/Exclusion Criteria

###### *A. Key Inclusion Criteria*

- age 18-65 years
- works 5 or more night shifts per month (each shift lasting at least 10 hours, with  $\geq 6$  hours worked between 10 pm and 8 am) with plans to maintain this schedule for the duration of the 3-week trial
- meets the criteria for SWD according to the International Classification of Sleep Disorders and evaluation of a sleep medicine provider (physician or nurse practitioner) during a screening evaluation:

a) affirmative answers to Do you experience excessive sleepiness? (yes/no); “Do you experience difficulties with falling asleep during opportunities for sleep? (yes/no); “Is the sleep or sleepiness problem related to a work schedule where you

have to work when you would normally sleep? (yes/no)”; and “Has this sleep or sleepiness problem related to your work schedule persisted for at least three months? (yes/no)

b) based on the evaluation of the sleep medicine provider, the sleep and/or wake disturbance are not better explained by another current sleep disorder, medical or neurologic disorder, mental disorder, medication use, poor sleep hygiene, or substance abuse disorder.

- Stable medication dosage over previous 4 weeks.
- Able to understand English and give a written informed consent document.

*B. Key Exclusion Criteria*

- Currently taking stimulant medications such as Modafinil, Armodafinil, Methylphenidate, or Dextroamphetamine.
- History of automobile accident due to falling asleep while driving
- Inability to understand or read English
- Self-reported Substance abuse (current)
- Excessive alcohol consumption defined as:
  - More than 3 glasses of wine a day
  - More than 3 beers a day
  - More than 60 mL of hard liquor a day
- Presence of cardiac pacemaker or automatic implantable cardioverter-defibrillator (AICD).
- Pregnancy, lactation (will be screened with urine pregnancy test)
- Non-removable metal or tattoos around head
- Use of implantable birth control device such as Implanon
- History of frequent severe headaches
- Unstable coronary artery disease
- Uncontrolled Seizure disorder
- Uncontrolled hypertension
- Any other clinically significant condition that, in the opinion of the Investigator, might put the subject at risk of harm during the study or might adversely affect the interpretation of the study data.

*b) Screening Procedures*

A screening visit will be scheduled to determine eligibility as above. A separate informed consent for the purpose of screening potential candidates will be obtained. Female patients of childbearing potential will be required to have a negative pregnancy test result at screening. Those with known sleep apnea are eligible for the study provided they are compliant with therapy (defined as > 4 hours of average nightly use for at least 30 days).

The modified neck circumference (MNC) score will be obtained during the screening visit. The MNC is calculated as the neck circumference measured in centimeters and adjusted if the patient has hypertension (4 cm is added), is a habitual snorer (3 cm is added), or is reported to choke or gasp most nights (3 cm is added). Those with an MNC score >48 cm water which indicates an increased risk of having obstructive sleep apnea (OSA) will have home sleep apnea testing (HSAT).

Those with an apnea-hypopnea index of  $\geq 15$ /hour based on the HSAT will be excluded and referred to their primary care physician for treatment discussion.

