## **C. Study Plan**

This is a preliminary single-arm study. The study will last up to 6 weeks including the screening period. Subjects will receive active tDCS for 30 minutes before their scheduled work hours at least 3x/week for two consecutive weeks.

Outcome measures will include: psychomotor vigilance test (PVT) and the Karolinska Sleepiness Scale (KSS) which will be obtained during the shift work.

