## **Visit Schedule**

### **A) Screening visit**

During this visit, the following will be obtained for all subjects:

- a. Screening Informed consent (if not obtained on a prior separate visit)
- b. Evaluation for SWD by investigator
- c. Pregnancy test, if applicable
- d. Height and weight
- e. Blood pressure and pulse rate
- f. Medication list
- g. Cognitive Tasks results
- h. Epworth sleepiness scale (ESS)
- i. CPAP compliance for those who are known to have sleep apnea
- j. MNC score
- k. HSAT, if applicable as explained above
- l. Expected visit length: 60 minutes**

The following are the reasons why subjects may not proceed with the study after screening:

- a) If they are determined to have significant sleep apnea, this will end their participation in this research study. The home sleep study results will be provided to research participants or their health care provider for referral for appropriate treatment.
- b) The investigators determine that the subject does not have shift work sleep disorder.

Those who remain eligible will then sign a separate informed consent for the remainder of the study. They will be requested to complete a baseline PVT and KSS during their shift work prior to the tDCS stimulation sessions. The PVT is a test that measures the speed with which subjects respond to a visual stimulus. It is a simple task where the subject presses a button as soon as the light appears. The light will turn on randomly every few seconds for 3 minutes. The KSS is a subjective measure of sleepiness. They will be provided with a mini-IPAD that contains the PVT and KSS apps. The PVT and KSS will only take 4 minutes and will be collected around 6 pm, 12 midnight and 4 am.

**B) Visit 1** (stimulation #1)

During this visit, the following will be obtained for all subjects:

- a. Study Informed consent (if not already obtained)
- b. Resting blood pressure and pulse rate
- c. Changes to Medication

They will then receive active tDCS for 30 mins. PVT **during** the active tDCS

- d. Side effects questionnaire **after** the active tDCS
- e. Actigraphy equipment will be provided to be worn throughout the duration of the study. Instructions on how to wear an actigraph device around their wrist that measures both the rest-activity cycle will be provided.
- f. **Expected visit length: 60 minutes**

**C) Visit 2** (stimulation #2)

During this visit, the following will be obtained for all subjects:

- a. Resting blood pressure and pulse rate

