- b. Changes to Medication

They will then receive active tDCS for 30 mins. PVT **during** the active tDCS

- a. Side effects questionnaire **after** the active tDCS
- b. **Expected visit length: 60 minutes**

**D) Visit 3** (stimulation #3)

During this visit, the following will be obtained for all subjects:

- a. Resting blood pressure and pulse rate
- b. Changes to Medication

They will then receive active tDCS for 30 mins. PVT **during** the active tDCS.

- c. Side effects questionnaire after the active tDCS
- c. PVT and KSS (6 pm, 12MN, and 4 am)
- g. **Expected visit length: 60 minutes**

**Visits 1-3 will occur during a one week period. Subjects will then be asked to obtain the KSS score and PVT during their shift work at 6 pm, 12 MN, and 4 am at the end of Visit 3.**

E) Visits 4, 5, 6 represent the second week of tCDS active stimulation and will be similar to Visits 1-3 with an expected visit length of 60 minutes per visit and will occur over a one-week period.

Subjects will be asked to obtain the KSS score and PVT during their shift work at 6 pm, 12 MN, and 4 am at the end of Visit 6. In addition, at the end of Visit 6, the following will be obtained **after** the active tDCS

- i. Cognitive Tasks results
- ii. Epworth sleepiness scale (ESS)

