**Visit Schedule**

Procedures	Visit #						
	S	1	2	3	4	5	6
Screening consent	x						
Study consent		x					
Medication list	x	x	x	x	x	x	x
Height and weight	x						
BP and Pulse rate	x	x	x	x	x	x	x
MNC	x						
HSAT, if applicable	x						
Pregnancy test, if applicable	x						
Cognitive tasks	x						x
ESS	x						x
Actigraphy		x	x	x	x	x	x
tDCS		x	x	x	x	x	x
Side-effects		x	x	x	x	x	x
*PVT		x		x			x
*KSS		x		x			x

\*obtained during the subjects' shift work at baseline at baseline prior to stimulation and after every 3 tdcS stimulation session

S= screening visit (requires a separate consent)

BP= blood pressure

MNC= modified neck circumference

HSAT= home sleep apnea test

tDCS= transcranial direct current stimulation

PVT= psychomotor vigilance test

KSS= Karolinska sleepiness scale

ESS= Epworth Sleepiness Scale

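### Pregnancy is an exclusion, but the only test is at screening, which the timeline allows to fall up to 4 weeks before the first stimulation

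*Combined protocol and SAP*

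**What the plan says.** In the combined protocol and SAP, the Key Exclusion Criteria (section III.B.1) list "Pregnancy, lactation (will be screened with urine pregnancy test" and give no timing for the test. The Vulnerable Populations section adds that fetuses are among the groups not studied.

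Timing is given in three places, which agree:
- The Screening Procedures text: "Female patients of childbearing potential will be required to have a negative pregnancy test result at screening".
- The Visit Schedule list for the screening visit, item c: "Pregnancy test, if applicable".
- The Visit Schedule table, where the pregnancy test row has one mark. The medication and blood pressure rows are marked at screening and at all six visits.

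The lists for Visits 1, 2 and 3 contain no pregnancy test, and Visits 4 to 6 are described as similar to them.

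On duration, section III.C (Study Plan) says "The study will last up to 6 weeks including the screening period" and "Subjects will receive active tDCS for 30 minutes before their scheduled work hours at least 3x/week for two consecutive weeks". Between screening and Visit 1, eligible subjects have a further step: "They will be requested to complete a baseline PVT and KSS during their shift work prior to the tDCS stimulation sessions". No maximum interval from screening to Visit 1 is stated.

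**The concern.** An exclusion is meant to hold when exposure begins. Most of the listed exclusions are stable over a few weeks, but pregnancy can newly arise between screening and Visit 1. The protocol re-checks blood pressure and medication changes at each stimulation visit, but not this.

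The interval also has real content. It holds the baseline shift for every subject and a home sleep apnea test for some. Subjects may work as few as 5 night shifts a month, while sessions must be placed before shifts at least three times a week for two weeks running, so a wait before Visit 1 is plausible.

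At stake is whether a safeguard that the sponsor chose to include works at the point where it matters. No endpoint, error rate or estimate depends on it.

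**Working it through.** The documents state no screening-to-Visit-1 window, so there is no figure to reproduce. The longest gap has to be derived.

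**Inputs**
- Total duration, screening included: up to 6 weeks (Study Plan).
- Stimulation: 2 consecutive weeks (Study Plan). The Visit Schedule agrees: "Visits 1-3 will occur during a one week period", and the second set of three visits "will occur over a one-week period", so 1 + 1 = 2 weeks.
- Pregnancy test: at the screening visit only.

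**Longest gap from test to first stimulation**

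Gap = total duration - stimulation period = 6 - 2 = 4 weeks.

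This assumes that the test is done at the start of the 6 weeks, that the whole allowance is used, and that stimulation fills its two weeks.

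**Check against the other duration in the document**

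The inclusion criteria speak of a 3-week trial without saying what the 3 weeks contain.
- If they are one baseline week plus two stimulation weeks, screening can take 6 - 3 = 3 weeks. The baseline week also precedes Visit 1, so the gap is 3 + 1 = 4 weeks, as before.
- If the 3 weeks included screening, the gap would be about 3 - 2 = 1 week. That reading conflicts with the 6 weeks that the Study Plan allows with screening included.

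**Consequence**

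Take a subject who tests negative at screening, becomes pregnant before Visit 1 and does not know it. She meets a stated exclusion at Visit 1, but no scheduled procedure would show it, and stimulating her would breach no written step.

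**The case against.** The strongest reply is that nothing here is contradictory. The criterion, the screening text, the visit list and the table all place the test at screening, and no section promises a re-check, so this is a preference about timing in a low-risk study. The protocol classes the device as non-significant risk and calls the study's risks minimal. It has six in-person visits, an investigator-judgement exclusion and a provision that subjects can withdraw or be withdrawn at any time. The consent pages are not in the public text, so any instruction there on contraception or on reporting a pregnancy cannot be assessed.

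Much of this stands. It limits the point to a pregnancy that nobody has recognised, and it keeps the severity low. It does not answer the point, because none of these provisions detects an unrecognised pregnancy or bounds the interval from test to exposure.

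It is also fair that 4 weeks is a ceiling. The second consent can be signed at Visit 1 and so need not add delay, and the home sleep apnea test applies only above a neck-circumference threshold.

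A reader might infer two stronger claims that should not be made:
- **That the test can be 6 weeks old at the last session, so subjects are unprotected throughout exposure.** The 6-week bound follows from the Study Plan, but a test tied to Visit 1 would still leave the two stimulation weeks untested. It is therefore not an argument for the change proposed here.
- **That a countable number of exposures is to be expected.** The documents give neither the number of women of childbearing potential nor a conception rate, so any such figure would rest on assumption alone.

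**Conclusion.** The point holds as a minor one. Pregnancy is excluded, its only test is at screening, no limit links that test to Visit 1, and the stated durations allow up to 4 weeks between the test and the first stimulation.

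The 4 weeks rest on the Study Plan's 6-week and 2-week figures and on testing at the start of screening. The documents give no typical gap. They support saying that an unrecognised pregnancy arising in that interval could go on to stimulation without a deviation. They do not support any statement about how often this would happen or about harm from it: they quantify no pregnancy-specific hazard. Power, error control and interpretation of the co-primary endpoints are unaffected.

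**What to change.** Reconcile the Screening Procedures text, the screening visit list and the schedule table with the exclusion criterion and the Vulnerable Populations statement, so that the existing urine test establishes eligibility at the start of stimulation. Either of two edits would do:
- re-time that test relative to Visit 1; or
- keep it at screening and state a maximum interval from test to Visit 1.

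The timing or interval is for the sponsor to choose.

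Re-timing adds no procedure. A stated maximum would require a repeat urine test only for subjects whose screening overruns it. The downside is that an occasional subject may be found ineligible after completing the baseline shift. The enrolment plan already allows for losses (45 x (1 - 0.40) = 27 evaluable), so the design, sample size and endpoints need not change.

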### d) **Modified Neck Circumference (MNC) score**

This will be obtained during the screening visit. The MNC is calculated as the neck circumference measured in centimeters and adjusted if the patient has hypertension (4 cm is added), is a habitual snorer (3 cm is added), or is reported to choke or gasp most nights (3 cm is added).

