### e) **Home sleep apnea testing (HSAT)**

This is part of the screening procedure. Subjects with an MNC score >43 cm high, indicating a moderate to high probability of having obstructive sleep apnea (OSA), will have home sleep apnea testing (HSAT). Those with an apnea-hypopnea index of  $\geq 15$ /hour based on the HSAT will be excluded and referred to their primary care physician or the sleep medicine clinic for treatment discussion. Subjects will be given a copy of the HSAT report. Subjects will be given instructions on how to use the HSAT equipment which is used routinely in clinical practice for home sleep apnea testing by clinical staff of the OSU Lung Center. The device will be preset to turn on automatically at home at the desired time. HSAT includes recordings of nasal pressure, thorax and abdominal movements, oxyhemoglobin saturation, and pulse rate. Subjects will be provided a telephone number to call should they have any questions about the device.

HSAT will be scored according to standard criteria. Briefly, an apnea is scored when all of the following criteria are met: a drop in airflow sensor excursion by > 90% of baseline, the duration of the event lasts at least 10 sec, and at least 90% of the event's duration meets the amplitude reduction criteria. An apnea is classified as obstructive if it is associated with continued or increased respiratory effort throughout the entire period of absent airflow, central if it is associated with absent respiratory effort throughout the entire period of absent airflow, and mixed if it is associated with absent respiratory effort in the initial portion of the event, followed by resumption of respiratory effort in the second portion of the event. A hypopnea is scored if the following criteria are met: the airflow signal excursion drops by >30% of baseline, there is a >4% desaturation from pre-event baseline, and at least 90% of the event's duration meets the amplitude reduction criteria.

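### The protocol gives two different neck-circumference scores, 48 and 43 cm, as the trigger for home sleep apnea testing at screening, and does not say which applies

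*Combined protocol and SAP*

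**What the plan says.** The protocol describes the sleep apnea screen in several places.

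- **Section III.B, Screening Procedures.** HSAT is required for "Those with an MNC score >48 cm water which indicates an increased risk of having obstructive sleep apnea (OSA"). An AHI of at least 15 per hour on that test leads to exclusion and referral.
- **Detailed Procedures, item e) HSAT.** The item says that the test belongs to screening and requires it for "Subjects with an MNC score >43 cm high, indicating a moderate to high probability of having obstructive sleep apnea (OSA"). The AHI exclusion limit is the same.
- **Detailed Procedures, item d) MNC score.** "The MNC is calculated as the neck circumference measured in centimeters and adjusted if the patient has hypertension (4 cm is added"), with 3 cm more if the person "is a habitual snorer (3 cm is added") and another 3 cm for choking or gasping on most nights. Screening Procedures defines the score in the same way. Item d) gives no cutoff.
- **Visit Schedule, A) Screening visit.** The list includes "HSAT, if applicable as explained above", without a number. It then says of candidates: "If they are determined to have significant sleep apnea, this will end their participation in this research study".
- **Visit Schedule table.** HSAT is marked at screening where applicable, again without a number.
- **Key Inclusion Criteria.** A sleep medicine provider must judge that "the sleep and/or wake disturbance are not better explained by another current sleep disorder".

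**The concern.** One screening step has two decision thresholds. For a score above 43 and up to 48, following one section means departing from the other, so staff cannot comply with both and a monitor cannot say whether a deviation occurred.

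The threshold matters because it decides who has the objective test. A candidate in this range with an AHI of at least 15 per hour would be found, excluded and referred under item e). Under Screening Procedures the same candidate, if every other criterion is met, could be enrolled without a test. The rule that significant apnea ends participation is of limited help here, since it depends on the apnea having been found.

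The unit is a second visible fault. The score is a length plus lengths, yet Screening Procedures states its cutoff in centimetres of water, a unit of pressure. That sentence therefore needs correction whichever number was intended.

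**Working it through.** The plan states no derived figure to reproduce. The check is a comparison of texts followed by subtraction.

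**1. Are these the same step?**

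| Feature | Screening Procedures (III.B) | Detailed Procedures, items d) and e) |
|---|---|---|
| Stage | Screening | Screening |
| Score | Neck in cm, +4, +3, +3 cm | Neck in cm, +4, +3, +3 cm |
| Trigger for HSAT | >48, pressure unit | >43 cm |
| Exclusion after HSAT | AHI ≥15/hour | AHI ≥15/hour |

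Only the trigger, its unit and the description of the risk differ. Both texts are current; neither is an amendment log.

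**2. Does other text settle it?** The screening visit list points to an explanation above it. The only trigger that precedes that list is the one in Screening Procedures, so by position the pointer leans that way. It gives no number, however, and does not set aside the separate rule in item e). The schedule table and item d) give no cutoff. The data safety monitoring plan mentions HSAT only as a minimal-risk procedure.

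**3. Who falls between the rules?** The gap in the score is 48 − 43 = 5 cm. If *a* is the sum of a person's adjustments, the measured neck circumference in the gap runs from above 43 − *a* up to and including 48 − *a*.

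| Adjustments | *a* (cm) | Measured neck in the gap (cm) |
|---|---|---|
| None | 0 | >43 to 48 |
| Snoring, or choking/gasping | 3 | >40 to 45 |
| Hypertension | 4 | >39 to 44 |
| Snoring and choking/gasping | 6 | >37 to 42 |
| Hypertension plus one other | 7 | >36 to 41 |
| All three | 10 | >33 to 38 |

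**4. How many people?** The documents give neither an MNC distribution nor an apnea prevalence, so this cannot be computed. As an illustration only, assume a normal score with mean 37 to 44 cm and SD 4 or 5 cm. The share in the gap is Φ((48 − mean)/SD) − Φ((43 − mean)/SD):

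| Assumed mean (cm) | SD 4 | SD 5 |
|---|---|---|
| 37 | 0.064 | 0.101 |
| 40 | 0.204 | 0.219 |
| 42 | 0.334 | 0.306 |
| 44 | 0.440 | 0.367 |

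- Of 45 planned: 45 × 0.064 = 2.9 to 45 × 0.440 = 19.8.
- Of 27 evaluable: 27 × 0.064 = 1.7 to 27 × 0.440 = 11.9.
- If 20% to 40% of those in the gap have an AHI of at least 15 per hour (also assumed): 27 × 0.064 × 0.2 = 0.3 to 27 × 0.440 × 0.4 = 4.8 of 27 would have different eligibility under the two rules.

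These figures ignore removal of candidates by the sleep provider, which would lower them, and do not model known, treated apnea. They are not estimates.

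**The case against.** The strongest reply is that little depends on this. The trial is a preliminary single-arm study whose primary analysis is a paired comparison of Visit 6 with baseline. Apnea that stays stable would be present at both times, so no bias or loss of power follows. The MNC score only selects people for a test, and the exclusion limit itself is stated consistently. There are other safeguards: the sleep provider's evaluation, the investigator's discretion to exclude any condition that could affect interpretation of the data, and the investigators' right to stop a candidate judged not to have shift work disorder. The screening visit's pointer also leans toward one of the two rules. Finally, the numbers differ by one digit and the text was extracted by program, so a misreading is possible.

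Much of this stands. No effect on the primary result is claimed. The safeguards lower the chance that apnea goes unnoticed, and the illustrative counts carry little weight. But none of the safeguards is a sleep test, and the protocol added a score-triggered test on top of them; that added step is the one left undefined. The pointer is a general cross-reference and does not override an operative rule elsewhere. A misread digit alone is an unlikely explanation, since the two sentences also differ in unit and in how they describe the risk. The source page should still be checked first.

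**Conclusion.** The concern holds: the trigger for HSAT is wrong as written and must be corrected. Two cutoffs 5 cm apart govern the same screening step, one of them in a unit that does not fit the score, and nothing in the protocol says which applies. The contradiction and the 5 cm gap rest on the text alone. The number of people affected is unknown. The illustrative range, from under 1 to about 5 of 27 with changed eligibility, rests wholly on assumed inputs, and the conclusion does not depend on it. What is harmed is consistent eligibility, the definition of the population studied, and detection and referral of people with an AHI of at least 15 per hour. The documents do not show which cutoff was intended, and this review takes no position on it.

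**What to change.** First check both sentences against the source pages. Then reconcile Screening Procedures (section III.B) and item e) of the Detailed Procedures to one cutoff, in centimetres and worded identically. The choice of value is for the sponsor and the investigators. It would help if the screening visit list and the Visit Schedule table cited that single rule by section, although neither contradicts anything now.

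If screening has already begun, report how many candidates scored above 43 and up to 48 cm, how many of them had HSAT, and how many were enrolled without it.

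The cost is a wording change in two places, or four with the cross-references. The number of home tests may change, but the test is already in the protocol. The planned sample size and the analysis are not affected.
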